8.26.3. Risk, burdens, and benefits

The PERMIT study is purely observational and will not affect any patient's treatment; however, parents / legal representatives will have the opportunity to withdraw the patient from the study at any time. All data collected before patients opt-out would be used only for study purposes and stored securely in accordance with Data Protection guidelines. This process will be known to them through leaflets and posters that will be accessible on the PICU written in a clear and understandable language. No identifiable information will be accessed directly for the study. It is often the case that those involved in the decision to participate in studies would like to see their data used to improve the care they and other patients are given.

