The majority of CYP will be unable to provide assent to participate (for example; because of their age (<1 year of age), on pain relief medications, sedated to tolerate interventions). Therefore, we will rely primarily on consent from parents/legal guardians. However, where possible and appropriate, the Local PERMIT Research Team will seek verbal or written assent from the CYP themselves at the time of recruitment. Where this was not possible and consent has already been obtained from their parent/legal guardian, the research team will approach at a later date to discuss the study and gain assent. Assent will be recorded on CYP assent form PERMIT_Child_Assent_Form_V1_07.12.2020), which will be completed with a member of the Local PERMIT Research Team with copies provided to parents/legal guardians and for the medical notes. During the assenting process, the Local PERMIT Research Team will ensure that CYP:

- Understand the purpose and nature of the research.
- Understand what the research involves, its benefits, risks and burdens.
- Understand the alternatives to taking part.
- Are able to retain the information long enough to make an effective decision.
- Are able to make a free choice.
- Are capable of making this particular decision at the time it needs to be made (recognising that their capacity may fluctuate, and they may be capable of making some decisions but not others depending on their complexity).

The Local PERMIT Research Team will employ a 'best interests' approach. Mental capacity will be assumed unless proven otherwise. All members of the Local PERMIT Research Team recruiting CYP into this study will have been trained in Mental Capacity Assessment as part of routine clinical training.

Parents/legal guardians and CYP may request withdrawal from the PERMIT feasibility study at any point, including during step 2 where they have agreed for their child to receive the PERMIT intervention. Reasons for withdrawal will be recorded in the screening logs at each PICU site. At the time of withdrawal we will ascertain if they wish to withdraw from ongoing involvement in the PERMIT intervention or if they wish for all their previously collected data to be removed.

13.11.7. Step 3:

PERMIT champions: The weekly debrief with consenting PERMIT champions will continue.

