Local sites will complete the validated data collection tools and CRFs listed in section 9.6.5 and the CYP clinical data section of the table at 9.6.11 (details in appendix 1) for all enrolled patients using the PERMIT study ID on each record.

Dependent on local site preference, the validated data collection tools and CRFs will be accessible both:

- Via direct electronic data entry (via web-accessed iPad or computer) to input directly into the secure REDCAP database using the PERMIT study ID for patient identification only; and/or
- Via paper-based format. Paper data collection tools and CRFs will be collated and stored in patient-specific site files. Local sites will be responsible for the safe and secure storage of these primary documents (locked in a filing cabinet or office within the PICUs or research offices). If not using iPads/computer direct entry, local sites will input paper-based data onto the REDCAP computer database using the PERMIT study ID for patient identification only. No identifiable patient data will be uploaded to REDCAP or shared with the PERMIT Trials Office at the University of Birmingham.

The Central PERMIT Research Team will access the de-identified data in the REDCAP database.

Data contained within REDCAP will be transferred securely to the University of Birmingham computer server within the PERMIT study database for statistical analysis in the PERMIT Trials Office at the University of Birmingham.

13.14.8. PERMIT intervention data (screening logs and CRFs):

The Local PERMIT Research Team will create an electronic screening log at each site to record all screening for eligibility for the PERMIT study. The log will include local patient IDs [NHS number and own hospital patient identification number]. This record will remain at the local site only and will not be shared with the Central PERMIT Research Team. For patients that fulfil **all** inclusion criteria and **no** exclusion criteria **and** consent is obtained from parents/legal guardians, local research staff will add the patient to the enrolment log.

PERMIT intervention data will be transferred from the CRFs and entered at the local site into the REDCAP database using the patient identification number with no identifiable information. Data contained within REDCAP will be transferred securely to the University of Birmingham computer server within the PERMIT study database for statistical analysis in the PERMIT Trials Office at the University of Birmingham.

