13.17.6. Serious adverse event reporting

All SAEs (other than those defined in the protocol as not requiring reporting) should be reported to the CI and Sponsor within 24 hours of the Local PERMIT Research Team at the individual PICU becoming aware of the event. SAEs will be reported using the SAE report form. The local team should not wait until all information about the event is available before notifying the CI of the SAE. Information not available at the time of the initial report must be documented and submitted as it becomes available. The CI will acknowledge receipt of the SAE Form within two working days by email to the Local PERMIT Research Team.

If, in the opinion of the PI or other medically qualified designee, an SAE occurring to a research participant is classified as:

- **Related:** that is, it resulted from delivery of the intervention, and
- **Unexpected:** that is, the type of event is not listed in the protocol as an expected occurrence

then the CI will be responsible for reporting the SAE to the sponsor and to the REC which issued the favourable ethical opinion. The CI will submit the SAE (using the SAE report for CTIMPs published on the Health Research Authority website) within 15 days of the PI becoming aware of the event.

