13.19.2. Central monitoring

The PERMIT Trials Office will be in regular contact with the Local PERMIT Research Team and PICANet to check on progress and address any queries that they may have. The PERMIT Trials Office will check the incoming summary of screened cases and CRFs for compliance with the protocol, data consistency, missing data, and timing. Sites will be asked for missing data or clarification of inconsistencies or discrepancies.

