13.21.4. Data monitoring and ethics committee (DMEC)

An independent DMEC has been appointed by the NIHR in keeping with standard structure and definitions. An independent DMEC will monitor recruitment and retention, adherence with the intervention and patient safety. Meetings will take place immediately prior to TSC meetings.

17/21/06: The PERMIT Feasibility Study

Title	First name	Last name	Job Title	Expertise
[name]	[name], Clinician, Trialist
[name]	Senior Statistician	Statistics
[name]	Paediatric Intensive Care consultant	Clinician

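### Data removal at withdrawal has no exception for safety data, and no stated route takes withdrawal reasons off site, so non-serious adverse events before a removal request could be lost from the safety summaries

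*Protocol*

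**What the plan says.** Protocol 13.11.6 (Step 2) allows withdrawal at any point, including after the family has agreed to the intervention. The team then finds out if the family wants only to stop further involvement or "if they wish for all their previously collected data to be removed". The same paragraph adds: "Reasons for withdrawal will be recorded in the screening logs at each PICU site".

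Protocol 13.14.8 describes that log, which holds NHS and hospital numbers, and says: "This record will remain at the local site only and will not be shared with the Central PERMIT Research Team".

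The CRF content listed in 13.13.6 covers acuity, prescribed and delivered activity, deviations, pause-and-reassess use, safety events and manual tailoring. It has no item for the date of or reason for withdrawal.

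Safety is objective (iv) in 13.9.2. It supplies two secondary outcomes in 13.12.2: event rates during an ERM activity and event rates over the whole study period. Section 13.20.3 plans the number of adverse events and the proportion of patients who have one. On oversight, 13.21.4 says: "An independent DMEC will monitor recruitment and retention, adherence with the intervention and patient safety".

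**The concern.** A family whose child was hurt or distressed during a rehabilitation session has a plausible motive both to withdraw and to ask for the data to be erased. If that happens, whether a child's record stays in the dataset depends on the outcome being measured. The child leaves both the numerator and the denominator of the adverse-event proportion, and the exposure that preceded the event goes too.

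The reason for withdrawal is the item that would reveal such a pattern, and it sits in a record that the protocol holds at the site. The adverse-event proportion is one of the figures on which the safety planning of a definitive trial would rest. A statistical analysis plan cannot repair this, because it cannot restore deleted records. The rule has to be set in the protocol and the consent documents.

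**Working it through.** **1. What happens to each item if 13.11.6 is followed as written.** The cases below are for a family that chooses data removal.

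- *Serious adverse event.* Under 13.17.6 the site has 24 hours from learning of an SAE to inform the chief investigator and sponsor. Nothing says that a submitted report is retracted, so the event is known centrally. The protocol does not say whether it still counts in the results table.
- *Non-serious adverse event.* It is recorded on the CRF, entered in REDCap (13.14.8) and written in the medical notes (13.17.5). Several of the events listed as expected in 13.17.5, such as discomfort or pain, ventilator asynchrony or unplanned removal of a line, may well be non-serious. REDCap is the source of the analysis data. No text keeps the record after a removal request, and none provides for taking it again from the notes.
- *Pause-and-reassess triggers and delivered ERM activity.* These are recorded on the CRF (13.13.6, 13.17.2), with no expedited route and no exception.
- *Fact of withdrawal.* It can be seen as the difference between children recruited (a primary outcome, 13.12.1) and children analysed.
- *Reason for withdrawal.* It is recorded in the site log. The one central route that might carry it is in 13.19.2: "The PERMIT Trials Office will check the incoming summary of screened cases and CRFs for compliance with the protocol, data consistency, missing data, and timing". The content of that summary is not specified.

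**2. How much one or two removals matter.** The plan states no adverse-event, withdrawal or removal rate, so there is no figure to reproduce and the event counts below are assumed. The one input from the protocol is n = 30 (3 PICUs × 10, section 13.11.3). With x children having an event, of whom r are removed, the reported proportion is (x − r)/(30 − r). Intervals are exact (Clopper-Pearson) 95%.

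| Assumed true count | Families of children with an event who request removal | Reported |
|---|---|---|
| 4/30 = 13.3% (3.8 to 30.7) | 1 | 3/29 = 10.3% (2.2 to 27.4) |
| 4/30 = 13.3% | 2 | 2/28 = 7.1% (0.9 to 23.5) |
| 3/30 = 10.0% (2.1 to 26.5) | 1 | 2/29 = 6.9% (0.8 to 22.8) |
| 3/30 = 10.0% | 2 | 1/28 = 3.6% (0.1 to 18.3) |
| 2/30 = 6.7% (0.8 to 22.1) | 2 | 0/28 = 0% (0 to 12.3) |
| 6/30 = 20.0% (7.7 to 38.6) | 2 | 4/28 = 14.3% (4.0 to 32.7) |

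**3. The opposite direction.** If s families of children *without* an event ask for removal, the proportion becomes x/(30 − s). With x = 4 and s = 2 this is 4/28 = 14.3%, against 13.3%. Two removals among children with an event therefore move the estimate down by 13.3 − 7.1 = 6.2 percentage points, while two among children without one move it up by 14.3 − 13.3 = 1.0 point. The small-sample effect is asymmetric, but the net direction depends on who asks.

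**The case against.** A reader might infer that withdrawals prompted by harm disappear from the safety results altogether. The protocol does not support that, for these reasons.

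- Removal is one of two options. A family that only stops further involvement leaves all earlier safety data in place.
- Serious events have a separate 24-hour route to the chief investigator and sponsor.
- Reported adverse events are in the medical notes, source documents are kept for at least 10 years (13.16), and the data safety monitoring committee may have direct access to source (13.19.3).
- An excess of withdrawals or adverse events can trigger on-site monitoring (13.19.1).
- The count of losses is visible against the number recruited.
- Some log information must leave the site, since recruitment proportions are a primary outcome and a summary of screened cases goes to the Trials Office. One cannot assert that reasons never travel, only that no text says they do.

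It is also tempting to cite the Phase 1b observational study, where "All data collected before patients opt-out would be used only for study purposes" (8.26.3), as a contradiction. It is not one. That study ran without consent, on an opt-out basis and with no identifiable data, so a different rule in a consented intervention study is not an inconsistency.

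Three further points are fair. The information sheet and consent form for parents are not at hand and may already say what is kept. How far to limit data withdrawal is an ethical choice, and the study has REC approval. The illustrated intervals overlap heavily, and the safety outcomes carry no decision threshold.

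All of this narrows the point without closing it. The SAE route covers serious events only. The notes are not the analysis dataset. At 10 children per site, one or two withdrawals need not count as excessive. The DMEC meets just before the steering committee, whose fixed meetings are at the start and after the study (13.21.3, 13.21.4), so its only scheduled look at patient data may come after any removal.

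**Conclusion.** The point holds in a limited form. As written, the protocol offers removal of all collected data with no exception for safety records. Non-serious adverse events, pause-and-reassess triggers and ERM exposure recorded before a removal request could therefore be lost from the summaries in 13.12.2 and 13.20.3. No stated route takes the reason for withdrawal to the central team or the DMEC.

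The size cannot be estimated from the document. On assumed counts, one or two removals among children with an event shift the proportion by about 3 to 7 percentage points in a sample of 30 (13.3% to 10.3% for one removal; 2/30 = 6.7% to 0/28 for two). This rests on at least one such family choosing removal over simply stopping. A bias towards apparent safety is plausible but not established, because removals by families of children without an event would push the other way, though by less. The matter is one for a cheap improvement and does not invalidate the study.

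**What to change.** 1. Add to the REDCap CRF, in de-identified form, the date of and reason for withdrawal, including whether it followed an adverse event. The identifiable screening log can stay at the site as now.
2. Report the number of withdrawals, their reasons and the number of data removals to the DMEC and in the final report.
3. State in 13.11.6, consistently with the consent documents and subject to REC agreement, that adverse-event, SAE, pause-and-reassess and ERM-exposure data recorded up to withdrawal are retained in de-identified form. Removal on request would remain available for all other data.

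The cost is wording in the protocol and information sheet and a small CRF addition. The one real downside is that families lose the option of erasing the safety part of the record. If the REC does not accept item 3, items 1 and 2 still let a reader see how many children were removed and, where a reason was given, why.

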13.12. Primary and secondary outcomes

13.12.1. Primary outcomes

- **Number of PICUs implementing PERMIT intervention:**
 - We will record the proportion of PICUs progressing from step 1 (PICU preparation) to step 2 (patient delivery).
 - We will also assess implementation progress within PICUs (e.g. barriers and facilitators to implementation) PICUs using the weekly debrief with PERMIT champions, the three brief online surveys of PICU health care professionals and the interviews with PICU health care professionals.
- **Proportion of eligible CYP recruited to receive the PERMIT intervention:**
 - Eligible patient numbers and proportion of eligible CYP recruited will be recorded at each PICU site.
- **Proportion of completed outcome assessment tools of eligible CYP:**
 - Proportion of CYP with 100% completed outcome measurement tools and >50% completed will be recorded at each PICU site.

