13.5. TRIAL SUMMARY

Title	Feasibility of implementing the Paediatric Early Rehabilitation/Mobilisation during Intensive care (PERMIT) intervention.
Short Title	PERMIT Phase 3 Feasibility Study
Sponsor Name and Reference	University of Birmingham REF RG_20-206
Funder Name and Reference	NIHR HTA 17/21/06
Study Design	Feasibility non-randomised, un-blinded intervention study
Overall Aim	
To assess the feasibility of implementing the PERMIT intervention over three steps:
 
Step 1: Implementing the PERMIT intervention within paediatric intensive care units (PICUs).
 
Step 2: Enrolling and delivering the PERMIT intervention to children and young people (CYP) in PICUs.
 
Step 3: Measuring outcomes and assessing the impact of the PERMIT intervention on CYP and parents/legal guardians.

Study Objectives	
Step 1:
 
 (i) Prepare PICUs to implement the PERMIT intervention. (ii) Assess barriers & facilitators to implementation. 
Step 2:
 
 (iii) Assess enrolment, recruitment and delivery of the PERMIT intervention to CYP. (iv) Monitor safety of the PERMIT intervention and related adverse events. 
Step 3:
 
 (v) Measure clinically important outcomes following delivery of the PERMIT intervention. (vi) Assess parent/legal guardian acceptability of the PERMIT intervention and future trial design.
Population & Inclusion Criteria	
Steps 1-3:
 
 ▪ Health care professionals and managers within PICU. 
Steps 2-3:

[figure not shown]
17/21/06: The PERMIT Feasibility Study

	
 ▪ CYP Inclusion: 
 ▪ Admitted to a participating PICU. ▪ Age 0 to <16 years at time of admission. ▪ Likely to remain within PICU on day 3 post admission. ▪ Consent by parent/legal guardian. Exclude: 
 ▪ Local decision by PICU health care professionals not to include CYP. 
Step 3:
 
Parents/legal guardians of CYP fulfilling criteria above.

Setting	
3 UK NHS PICUs:
 
 ▪ University Hospital Southampton NHS Foundation Trust (Southampton Children’s hospital). ▪ King’s College Hospital NHS Foundation Trust, London. ▪ Birmingham Women & Children’s NHS Foundation Trust.

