In conjunction with patient's clinical team, the local PERMIT Research Team will screen and recruit CYP to receive the PERMIT intervention. They will screen all CYP admitted to each PICU against the study inclusion and exclusion criteria and record the screening and all related decisions in the screening log at each site. They will approach the parents/legal guardians of eligible CYP on day 1 or 2 of admission (where possible). They will explain the study and provide the participant information sheet (PERMIT_Parent_Legal_Guardian_Participant_Information_Sheet_A_V1_07.12.2020).

After providing time for parents/legal guardians to read the information and consider the study, the Local PERMIT Research Team will return to ask for consent for the CYP to take part in the study using the consent form (PERMIT_Parent_Legal_Guardian_Consent_Form_A_V1_07.12.2020). They will discuss the different options for consent. At this point, parents/legal guardians can choose between the following:

- Consenting for CYP to receive the PERMIT intervention, with accompanying data collection (specifically, CYP clinical data, PERMIT intervention data and safety monitoring). No additional requirements for parents/legal guardians.
- If they consent to the PERMIT intervention, they can also consent to complete additional outcome measurement tools (e.g. related to quality of life, fatigue, pain).
- If they consent to the PERMIT intervention and complete additional outcome measurement tools, they can also consent to an optional interview to assess acceptability.

Consent from parents/legal guardians will be obtained by a member of the Local PERMIT Research Team, with copies provided to the parents/ legal guardians and for the medical notes.

We will obtain consent to receive the PERMIT intervention from a parent/legal guardian and assent from the CYP where possible at the time of recruitment.

17/21/06: The PERMIT Feasibility Study

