 4. **The COMFORT behaviour scale (COMFORT-B scale)** is widely used in paediatric intensive care units to assess young children's pain and distress for those in receipt of analgesic and sedative medications. The COMFORT-B scale consists of six behavioural items: alertness, calmness, respiratory response (for ventilated children) or crying (for spontaneously breathing children), body movements, facial tension and muscle tone. Each item has five response alternatives rated 1 to 5 describing the different intensities of the behaviour in question. Summating the six ratings leads to a total score theoretically ranging from 6 to 30 (65). It has good validity and reliability properties (66).
 5. **Parent Stressor Scale: PICU (Revised)** (67). The PSS:PICU scale is designed to measure the response of parents to the potential sources of stress when their child is hospitalized in a PICU. It consists of 39 items organized into seven subscales: (a) appearance of the child (3 items); (b) sights and sounds (4 items); (c) procedures (7 items); (d) professional staff communication (5 items); (e) behavioral and emotional responses from the child (10 items); (f) behavior of staff (4 items); and (g) parental roles (6 items). The coefficient for all of the seven subscales was above 0.73, except for sight and sound (68)
 6. **The EMpowerment of PArents in The Intensive Care - 30 Item Version (EMPATHIC-30)** consists of 30 statements designed to measure parental experiences and satisfaction with care provided by nurses and doctors(15). It is divided into five domains: information (5 items), care and treatment (8 items), parental participation (6 items), organisation (5 items) and professional attitude (6 items). Responses are provided on a six-point scale ranging from 1 certainly no to 6 certainly yes. A domain mean score of greater than 5 is considered acceptable. A separate box labelled not applicable is available for all statements (69).
 7. **PedsQL™ 4.0 (Pediatric Quality of Life Inventory) Generic Core Scales and Infant Scales – Acute Version** measures health-related quality of life (HRQOL) in children and adolescents aged 1 month to 17 years old. The PedsQL™ Generic Core Scales are used for children ≥ 2 years of age. They are 23-item child self-report and parent proxy-report scales with four domains: physical functioning, emotional functioning, social functioning, and school functioning. The informant is
-

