8. **PedsQL™ Multi-dimensional Fatigue Scale – Acute Version** (84) is an 18-item scale that encompasses three domains: (1) General Fatigue (6 items, e.g., “I feel tired.”; “I feel too tired to do things that I like to do.”), (2) Sleep/Rest Fatigue (6 items, e.g., “I feel tired when I wake up in the morning.”; “I rest a lot.”), and (3) Cognitive Fatigue (6 items, e.g., “It is hard for me to keep my attention on things.”; “It is hard for me to remember what people tell me.”). The instructions ask how much of a problem each item has been during the past 7 days.(85) The PedsQL™ Multidimensional Fatigue Scale comprises parallel child self-report and parent proxy-report formats. Child self-report include ages 8–12, and 13–17 years. Parent proxy-report includes ages 2–4 (toddler), 5–7 (young child), 8–12 (child), and 13–17 (adolescent), and assesses parent’s perceptions of their fatigue. Cognitive functioning for infants 1-24 months are included in the PedsQL Infant Scale. Items for each of the forms are essentially identical, differing in developmentally appropriate language, or first or third person tense. The format, instructions, Likert response scale, and scoring method are identical to the PedsQL™ 4.0 Generic Core Scales, with higher scores indicating better HRQOL (lower fatigue symptoms).(84-88)
9. **PedsQL™ Pediatric Pain Questionnaire** is a generic symptom-specific instrument to measure pain in patients with acute and chronic health conditions. We will use question #1 and #2, which asks participants capable of self-reporting to identify a point on a 100 mm line that best shows the worst pain the subject experienced ‘now’ and ‘in the past week’. Anchors include “no hurting, no discomfort, or no pain” and “hurting a whole lot, very uncomfortable, severe pain”.
10. **Pediatric Cerebral Performance Category (PCPC)** and the **Pediatric Overall Performance Category (POPC)** quantify short-term cognitive impairments and functional morbidity.(89, 90) The POPC scale is dependent on the PCPC scale, as the PCPC status is included in POPC. Scores range from 1 to 6 for both scales with 1: good, 2: mild disability, and 6: brain death. Studies of patients with scores of 1–4 at PICU discharge, hospital discharge, and one- and six-month follow-up show association with the Stanford Binet Intelligence Quotient, Bayley scales, and Vineland Adaptive Behaviour Scale. (89-92).

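### Primary outcome 3 conflicts with the protocol's own age ranges for its instruments, and its heading uses a denominator that precedes consent

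*Protocol*

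**What the plan says.** Section 13.12.1 heads the third primary outcome "Proportion of completed outcome assessment tools of eligible CYP". The line beneath gives the measure: "Proportion of CYP with 100% completed outcome measurement tools and >50% completed will be recorded at each PICU site". No target or progression rule is attached to either threshold.

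The trial summary (13.5) admits children of "Age 0 to <16 years at time of admission". Section 13.13.7 asks parents, as proxies, for PedsQL and the Fatigue Scale at both time points, and for the Pain Questionnaire at the second. PedsQL is split into an infant form (1-23 months) and a form from 2 years. The Fatigue Scale has no age limit, either there or in the data collection table (13.13.10).

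Appendix 1 (13.25.1) says that PedsQL "measures health-related quality of life (HRQOL) in children and adolescents aged 1 month to 17 years old". Of the Fatigue Scale it says "Parent proxy-report includes ages 2–4 (toddler), 5–7 (young child), 8–12 (child), and 13–17 (adolescent"; for infants it only points to the cognitive items of the PedsQL Infant Scale. It describes the Pain Questionnaire as answered by children able to report for themselves.

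The tools are an optional tier of consent (13.11.6): "If they consent to the PERMIT intervention, they can also consent to complete additional outcome measurement tools".

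**The concern.** This is the only primary outcome that addresses whether outcomes can be collected, which is the Step 3 aim. It should show how often families complete the tools they are given. Two features of the definition affect the result for other reasons.

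First, the scheduled set includes tools for which the protocol describes no form at some enrolled ages, and nothing says how such a tool counts. Second, the heading's denominator takes in children whose parents declined the study or did not agree to the tools.

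A low figure could then reflect a young sample, slow recruitment or refusal of the optional tier. A reader planning the definitive trial could take it as poor completion.

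**Working it through.** The protocol states no expected completion proportion, so there is no figure to reproduce. The check is a count of tools by age, followed by the ceiling that each denominator imposes.

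**Step 1. Scheduled administrations (13.13.7 and 13.13.8).**
- Child tools: PedsQL 2 + Fatigue Scale 2 + Pain Questionnaire 1 = 5.
- Parent tools: Family Impact Module 2 + Parent Stressor Scale 1 + EMPATHIC-30 1 + PHQ-4 1 = 5.

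**Step 2. Administrations available by age, using the Appendix 1 age ranges.** The Pain Questionnaire is shown both ways because its respondent is contradictory.

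| Age | Pain tool answered by | Child tools | Child and parent tools |
|---|---|---|---|
| 2 years and over | either | 5/5 = 100% | 10/10 = 100% |
| 1-23 months | proxy | 3/5 = 60% | 8/10 = 80% |
| 1-23 months | self-report only | 2/5 = 40% | 7/10 = 70% |
| Under 1 month | proxy | 1/5 = 20% | 6/10 = 60% |
| Under 1 month | self-report only | 0/5 = 0% | 5/10 = 50% |

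The row for 2 years and over assumes the child can self-report where that is required. On a fixed-set reading, no row under 2 years reaches 100%. On child tools alone, a child under 1 month fails >50% either way; one aged 1-23 months fails it only if the pain tool is self-report.

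**Step 3. Ceiling on the 100% threshold.** With 30 recruited (13.11.3) and a share f under 2 years, the ceiling is 30 x (1 - f). The protocol gives no age distribution, so f is assumed:
- f = 0.2: 30 x 0.8 = 24 (80%)
- f = 0.4: 30 x 0.6 = 18 (60%)
- f = 0.6: 30 x 0.4 = 12 (40%)

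**Step 4. What eligible means.** The trial summary lists "Consent by parent/legal guardian" as an inclusion criterion, so the word could mean consented. Four other places use it for children before consent:
- Primary outcome 2, in the same section, is the share of eligible children who are recruited. If eligibility already required consent, it would be close to 100% by construction.
- Section 13.11.3 describes parents who decline although their child meets the eligibility criteria.
- Section 13.11.6 has staff approach parents of eligible children to seek consent.
- Section 13.13.6 counts eligible patients separately from those approached, consented and declined.

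**Step 5. Effect of the denominator.** With every tool completed by every tool-consenting family, and leaving age aside, the figure over eligible children is (recruited/eligible) x (tool consent/recruited). Neither rate is in the protocol. Assuming 50% and 80%, 0.5 x 0.8 = 0.40. In counts, 60 eligible give 30 recruited and 24 tool-consenting, all complete:
- 24/60 = 40% of eligible
- 24/30 = 80% of recruited
- 24/24 = 100% of tool-consenters

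Over wider assumed ranges (recruitment 30-90%, tool consent 50-100%), the ceiling runs from 0.3 x 0.5 = 15% to 0.9 x 1.0 = 90%. If 40% are also under 2, multiplying by 0.6 gives 9% to 54%.

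**Step 6. Descriptions that disagree.**
- Pain Questionnaire respondent: parent proxy in 13.13.7, child self-report in Appendix 1.
- Pain Questionnaire length: 1 item in 13.13.10, two questions in Appendix 1.
- Parent Stressor Scale: 30 items in 13.13.10. Appendix 1 says "It consists of 39 items organized into seven subscales", and its subscales confirm this: 3 + 4 + 7 + 5 + 10 + 4 + 6 = 39.

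**The case against.** The best defence is that completion naturally means all tools that apply at the child's age. The protocol already selects the PedsQL form by age, refers to Appendix 1, and promises a full statistical analysis plan that could set scoring rules. That is a reasonable guess at the intent. But the text that splits PedsQL by age leaves the Fatigue Scale unrestricted, so the written schedule contradicts the appendix. An analysis plan would have to override the protocol, not merely fill it in.

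On the denominator, the operational line says only children, not eligible children, and section 13.20.3 names no denominator. The wording is therefore ambiguous. The heading is nevertheless the only place a denominator is named, and the same section uses that word in its pre-consent sense. Section 13.11.7 also has staff re-approach parents who agreed only to the intervention. That should raise tool consent, but it leaves consent to the tools optional.

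A reader might infer that the outcome cannot measure completion at all. The documents do not support that. The >50% proportion is recorded too, no pass mark applies, screening and consent counts are kept, and section 13.20.2 plans a separate look at completeness and systematic missingness. Completion could be derived from the data collected.

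A reader might also let the item-count mismatches move the thresholds. Section 13.12.1 refers to completed tools and states no item-level rule, so they remain discrepancies to correct.

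**Conclusion.** The point holds as a mis-specification of a primary outcome. The part about age rests only on the protocol's text: no child under 2 can meet the 100% threshold as scheduled, and none under 1 month can pass >50% on child tools. Two tools certainly lack a form at some enrolled ages: the Fatigue Scale under 2 years and PedsQL under 1 month. A reader might count the Pain Questionnaire as a third, but the protocol contradicts itself on who answers it.

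The size in practice depends on assumed inputs. The ceiling of 24 down to 12 of 30 follows from an assumed 20-60% under 2. The assent paragraph in 13.11.6 mentions age under 1 year only as one reason why assent may not be possible, so it does not support any particular share. The 40% illustration depends on the assumed recruitment and tool-consent rates and on reading eligible as pre-consent.

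The risk is an understated or uninterpretable feasibility figure; no data would be lost.

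**What to change.** - **Numerator (13.12.1).** Define completion as all age-applicable tools at each time point, recorded at the existing 100% and >50% thresholds. State whether the parent tools count. If they do not, and the pain tool proves to be self-report, a child under 1 month has no applicable tool; say how such a child is handled.
- **Denominator (13.12.1).** Use recruited children, and also report the proportion among those whose parents consented to the tools. The first figure includes refusal of the tools; the second isolates completion. Do not use all eligible children, since primary outcome 2 already covers recruitment.
- **Schedule (13.13.7 and 13.13.10).** Limit the Fatigue Scale to ages 2 years and over, and state that PedsQL does not apply under 1 month.
- **Descriptions (13.13.7, 13.13.10 and Appendix 1).** Reconcile who answers the Pain Questionnaire, without presuming either version. Make its item count (1 or 2) and that of the Parent Stressor Scale (30 or 39) agree.

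The cost is a protocol wording amendment, with no extra patients and no new data.
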